### Research Protocol Lung Institute Dallas

- **Administration of incorrect stem cells** – The stem cells administered are the recipients own stem cells. There is a low risk of administration errors. Materials are clearly marked before they leave the procedure room, eliminating the risk of a recipient receiving someone else's stem cells in error.
- **Unintended differentiation** - The unintended differentiation of stem cells was found in a single study in which extensive intra-myocardial calcification after unselected bone-marrow cells transplantation was seen in the peri-infarct and infarct areas in rats. Though a low risk, unintended differentiation could occur in areas of stem cell implantation.

The following lists the potential benefits of treatment:

- **Increased Activity** - Ability to be more physically active; walking greater distances.
- **PFT** - Improvement in their FEV1 5-10% or more.
- **Oxygen** - Ability to reduce their use of oxygen and possibly to stop it.
- **Reduction in Medications** - Ability to function well without the use of their bronchodilator inhalers and Prednisone.
- **Increased Pulmonary Health** - Reduction or ceasing of secondary pulmonary infections

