10Mar2016 - version 2.0

LI-001

17.	
Clinic Staff takes blood supply to lab for processing and notifies Practitioner of Patient readiness.
 
 
• Has Clinic Staff completed the following? 
 
✓ Notified Practitioner of Patient readiness;
 
✓ Transfer blood drawn to the correctly labeled Harvest PRP cup for centrifuging; and
 
✓ Place PD Cup in centrifuge and press green start button or PRP start button.
 
 
 
 
➤ If NO > Step must be completed prior to proceeding.
 
➤ If YES > Proceed to Step 18 of this SOP

18.	
Practitioner reviews and conducts required pre-procedural protocols and renders physical exam.
 
 
• Has Practitioner reviewed the following prior to procedure and conducted the required? 
 
✓ Has Practitioner conducted and noted H&P or SOAP (Subjective; Objective; Assessment; Plan) on the Patient record; and
 
✓ Reviewed all required pre-procedural documentation?
 
 
 
 
➤ If NO > Step must be completed prior to moving forward with procedure.
 
➤ If YES > Proceed to Step 19 of this SOP

19.	
Clinic Staff will extract venous final product.
 
 
• Has Clinic Staff completed the following? 
 
✓ Draw PRP from the side compartment of PRP cup, identified by the white port.
 
✓ Use PRP to wash walls of PD Cup at least twice; and
 
✓ Extract into a 20ml syringe
 
 
 
 
➤ If NO > Step must be completed prior to proceeding.
 
➤ If YES > Proceed to Step 20 of this SOP

20.	
Clinic Staff administers final product.
 
 
• Has Clinic Staff completed the following? 
 
✓ Place venous final product (injected via the 20ml syringe referenced above) into the IV bag; and
 
✓ Open IV line (checking for sufficient flow and drip rate)
 
 
 
 
➤ If NO > Step must be completed prior to proceeding.
 
➤ If YES > Proceed to Step 21 of this SOP

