21.	
Clinic Staff conducts on-going oversight of Patient during administration.
 
 
• Has Clinic Staff confirmed the patency and flow are correct?
 
 
➤ If NO > Step must be completed prior to proceeding.
 
➤ If YES > Proceed to Step 22 of this SOP

22.	
Clinic Staff starts nebulizer treatment.
 
 
• Has Clinic Staff completed the following? 
 
✓ Place glutathione and saline into nebulizer medicine cup and provide Patient with instructions to begin nebulizing treatment; and
 
 
 
 
➤ If NO > Step must be completed prior to proceeding.
 
➤ If YES > Proceed to Step 23 of this SOP

10Mar2016 - version 2.0

LI-001

23.	
Clinic Staff discontinues IV line and nebulizer; and provide post care instructions.
 
 
• Has the Clinic Staff completed the following? 
 
✓ Turn off nebulizer when treatment completed;
 
✓ When final product has emptied IV bag, use normal saline flush to flush entire contents of IV line;
 
✓ Remove IV catheter;
 
✓ Place 2x2 gauze pad over site, affix coban bandage;
 
✓ Instruct Patient to remove gauze and coban after 20 to 30 minutes; and
 
✓ Dispose of supplies in designated biohazard containers.
 
 
 
 
➤ If NO > Step must be completed prior to proceeding.
 
➤ If YES > Proceed to Step 24 of this SOP

-----	---

24.	
Has Clinic Staff provides Patient with discharge folder and post-care instructions and answered any Patient questions or concerns?
 
 
• Has Clinic Staff advised the Patient of the below post-care instructions and ensured that they understand said instructions; answering any questions or concerns? 
 
✓ Briefly review and explain the discharge folder contents to Patient;
 
✓ Review LI follow-up procedures; and
 
✓ Review Patient Journals for quality of life outcome data.
 
 
 
 
➤ If NO > Step must be completed prior to proceeding.  ➤ If YES > Proceed to Step 25 of this SOP

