4.	
Clinic Staff must properly prepare and label syringes and supplies for Patient procedure.
 
 
• Has the Clinic Staff completed the following in the lab area? 
 
✓ Open Harvest PRP (PC-60) Kit;
 
✓ Label syringes and supplies w/ Patient Name and D/O/B;
 
✓ Draws 8ml ACD-A into 60ml syringe; and
 
✓ Spike 100ml IV bag with filter tubing to be used for administration of final product.
 
 
 
 
➤ If NO > Preparation is required prior to proceeding.
 
➤ If YES > Proceed to Step 5 of this SOP

5.	
Clinic Staff must properly prepare mayo stand under aseptic technique for Patient Bone Marrow procedure.
 
 
• Has the Clinic Staff prepared the mayo stand and procedure room with Harvest BMAC kit and by ensuring all the following is made available? 
 
✓ Harvest BMAC kit
 
✓ Marcaine/Bupivacaine 0.25%
 
✓ Heparin 1,000units/ml
 
✓ Anesthesia Syringe
 
 
 
 
➤ If NO > Preparation is required prior to proceeding.
 
➤ If YES > Proceed to Step 6 of this SOP

6.	
Clinic Staff must properly prepare mayo stand under a clean technique for Patient Venous procedure.
 
 
• Has the Clinic Staff prepared the mayo stand by covering with underpad and ensuring all the following is made available? 
 
✓ 60ml Syringe with ACD-A
 
✓ 20g or 22g IV Catheter
 
✓ IV Catheter Hep-Lock
 
✓ Alcohol Prep Pad(s)
 
✓ 2x2 Gauze
 
✓ IV Starter Kit
 
 
 
 
➤ If NO > Preparation is required prior to proceeding.
 
➤ If YES > Proceed to Step 7 of this SOP

7.	
Clinic Staff assumes responsibility of Patient and Patient care from the Office Manager.
 
 
• If Patient is on O, has Patient been transferred to clinic's oxygen concentrator for the remainder of the day's visit?
 
 
➤ If applicable, and NO > Transfer Patient as required prior to moving forward with SOP.
 
➤ If not applicable; or applicable, and YES > Proceed to Step 8 of this SOP

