15.	
Practitioner reviews and conducts required pre-procedural protocols and renders physical exam.
 
 
• Has Practitioner reviewed the following prior to procedure and conducted the required? 
 
✓ Has Practitioner conducted and noted H&P or SOAP (Subjective; Objective; Assessment; Plan) on the Patient record; and
 
✓ Reviewed all required pre-procedural documentation?
 
 
 
 
➤ If NO > Step must be completed prior to moving forward with procedure.
 
➤ If YES > Proceed to Step 16 of this SOP

16.	
Clinic Staff will extract venous final product.
 
 
• Has Clinic Staff completed the following? 
 
✓ Remove approximately 10-15ml plasma from white port of PD Cup using Harvest kit syringe with yellow stoppers and discard to appropriate biohazard container;
 
✓ Draw PRP from the side compartment of PRP cup, identified by the white port.
 
✓ Use PRP to wash walls of PD Cup at least twice; and
 
✓ Extract into a 20ml syringe and place labeled syringe on top of clean box for re-infusion once bone marrow extraction is complete.
 
 
 
 
➤ If NO > Step must be completed prior to proceeding.
 
➤ If YES > Proceed to Step 17 of this SOP

MATERIAL	Amount Required
BMAC Harvest kit (BMAC – 60-07)	1

17.
	
Has Practitioner ensured all of the following Reagents and Materials availability and prepare for procedure?
 
 
• Has Practitioner washed hands according to hand washing hygiene protocol?
 
• Has Practitioner dressed in appropriate PPE (Personal Protective Equipment)? 
 
✓ Gown
 
✓ Shoe Covers
 
✓ Hair/Head Cover
 
✓ Mask
 
✓ Gloves (to be donned upon right before commencement of procedure)
 
 
 
• Has Practitioner ensured all of the following Reagents and Materials availability and prepare lab space for procedure?
 
 
REAGENTS:
 
 
✓ Marcaine/Bupivacaine 0.25%
 
✓ Heparin 1,000units/ml
 
 
MATERIALS:
 
➤ If NO > Materials required must be available and prepared prior to proceeding.
 
➤ If YES > Proceed to Step 18 of this SOP

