
18.
	
Practitioner and an additional member of Clinic Staff (minimum of 2) will conduct and document on the Medical Record a “Time-Out”.
 
 
• Has the procedure team conducted pre-op verification check-point with an alert and aware Patient? 
 
✓ Patient Name
 
✓ DOB (Date of Birth)
 
✓ Procedure Type
 
✓ Allergies
 
✓ Anesthesia
 
✓ Procedure Site/Side & Process
 
 
 
 
➤ If NO > Time-Out must be completed and documented prior to proceeding.
 
➤ If YES > Proceed to Step 19 of this SOP

19.
	
Clinic Staff administers prophylactic antibiotic injection.
 
 
• Has Clinic Staff administered Rocephin? 
 
✓ Inject Rocephin 1g IM (Intra Muscular) via gluteus maximus; or
 
✓ In event of Penicillin (PCN) allergy, administer Lincocin 600mg IM via gluteus maximus.
 
 
 
 
➤ If NO > Step must be completed prior to proceeding.
 
➤ If YES > Proceed to Step 20 of this SOP

20.
	
Practitioner instructs Patient on safety protocol.
 
 
• Has Practitioner instructed Patient of lateral decubitus positioning? 
 
✓ Patient is placed on right or left side-lying position depending on patient preference; if applicable.
 
 
 
 
➤ If NO > Instruct Patient on safety protocol prior to proceeding.
 
➤ If YES > Proceed to Step 21 of this SOP

21.	
Has Practitioner checked on Patient readiness in the procedure room and noted Start-Time of Procedure once ready to commence procedure?
 
 
• Patient Readiness 
 
✓ Is Patient comfortable?
 
✓ Does Patient need anything?
 
✓ If Applicable, do we have Patient preferred music playing?
 
✓ If Applicable, is their O on?
 
 
 
• Start-Time 
 
✓ Note the Start-Time of Procedure
 
 
 
 
➤ If NO > Step must be completed prior to proceeding.
 
➤ If YES > Proceed to Step 22 of this SOP

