38.	
Clinic Staff prepares final product for administration via IV bag.
 
 
• Has Practitioner completed the following? 
 
✓ Remove 20ml syringe of bone marrow final product from Adi-Light;
 
✓ Inject bone marrow final product into 100ml normal saline IV bag; and
 
✓ Inject 20ml PRP syringe from top of clean box into same 100ml normal saline IV bag.
 
 
 
 
➤ If NO > Step must be completed prior to proceeding.
 
➤ If YES > Proceed to Step 39 of this SOP

39.	
Clinic Staff administers final product via IV.
 
 
• Has Clinic Staff completed the following? 
 
✓ Clean Hep-Lock site with alcohol prep pad;
 
✓ Affix IV tubing of final product contents to Hep-Lock catheter;
 
✓ Open IV line (checking for proper flow and drip rate).
 
 
 
 
➤ If NO > Step must be completed prior to proceeding.
 
➤ If YES > Proceed to Step 40 of this SOP

40.	
Clinic Staff conducts on-going oversight of Patient during administration.
 
 
• Has Clinic Staff confirmed the patency and flow are correct?
 
 
➤ If NO > Step must be completed prior to proceeding.
 
➤ If YES > Proceed to Step 41 of this SOP

41.	
Clinic Staff discontinues IV line.
 
 
• Has Clinic Staff completed the following? 
 
✓ When final product has emptied IV bag, use NS (normal saline) flush to flush entire contents of IV line;
 
✓ Remove IV catheter;
 
✓ Place 2x2 gauze pad over site, affix coban bandage
 
✓ Instruct Patient to remove gauze and coban after 20 to 30mins; and
 
✓ Dispose of supplies in designated biohazard containers.
 
 
 
 
➤ If NO > Step must be completed prior to proceeding.
 
➤ If YES > Proceed to Step 42 of this SOP

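### Section 13 says marking materials eliminates the risk of receiving another person's cells, yet from spun cup to infusion no SOP step shown matches the product label to the patient

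*Combined protocol and SAP*

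**What the plan says.** Section 13 (Risk and Benefit Analysis) has a bullet on administration of incorrect stem cells. It notes that the cells are the recipient's own and rates the chance of an administration error as low. It then says that materials are marked before leaving the procedure room, "eliminating the risk of a recipient receiving someone else's stem cells in error". Section 13 introduces its list as the risks given in the informed consent.

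The SOPs attached under policy CL-005 contain these controls:

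- **Labelling.** Each infusion SOP has a preparation step, for example "Clinic Staff must properly prepare and label syringes and supplies for Patient procedure", which puts name and date of birth on syringes and supplies in the lab area (venous Steps 4 and 7, discharge Step 5, bone marrow Step 4).
- **Cup.** Drawn blood goes into a cup described as correctly labelled (venous Step 17, discharge Step 9, bone marrow Step 14).
- **Held PRP syringe.** Bone marrow Step 16 tells staff to "place labeled syringe on top of clean box for re-infusion once bone marrow extraction is complete".
- **Time-Out.** Bone marrow Step 18 asks "Has the procedure team conducted pre-op verification check-point with an alert and aware Patient". Its items are name, date of birth, procedure type, allergies, anesthesia, and site and process.
- **Infusion.** Venous Step 20 and discharge Step 11 read "Place venous final product (injected via the 20ml syringe referenced above) into the IV bag". Bone marrow Step 38 puts the marrow product into a bag and then adds "Inject 20ml PRP syringe from top of clean box into same 100ml normal saline IV bag". The oversight step in all three pathways asks "Has Clinic Staff confirmed the patency and flow are correct".

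**The concern.** The protocol claims that a risk is removed by a measure that can only lower it. A label records whose product a syringe holds. It stops a wrong infusion only when someone compares it with the person about to receive the product. The SOPs are sequential checklists, so a check they do not list is not one they require.

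A participant could receive another person's cells in a study where every product is meant to be autologous, and no step shown is designed to catch this before the line is opened. Section 11e requires near-misses to be reported, but a label mismatch becomes a near-miss only if someone looks for it. Safety is the first research question (section 4).

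**Working it through.** The plan gives no figure to reproduce. The check is a reading of every step from the draw to line removal in the three SOPs that infuse a product, looking for any comparison of product label with patient.

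| Pathway | Up to the spun cup | From spun cup to infusion | Label-to-patient check after the spin |
|---|---|---|---|
| Venous | Supplies labelled (4 or 7); blood drawn (15 or 16); labelled cup (17) | Product drawn into 20 ml syringe (19); injected into bag, flow and drip rate checked (20); patency and flow checked (21) | None |
| Venous, discharge day | Supplies labelled (5); blood drawn (8); labelled cup (9) | 20 ml syringe (10); injected into bag, flow and drip rate checked (11); nebulizer (12); patency and flow checked (13) | None |
| Bone marrow | Supplies labelled (4); blood drawn and spun (13-14); labelled PRP syringe set aside (16); Time-Out (18); marrow harvested (29) and spun (35) | Concentrate into 20 ml syringe (36); 20 minutes in the light unit (37); two syringes pooled in one bag (38); Hep-Lock cleaned, line connected, flow and drip rate checked (39); patency and flow checked (40) | None |

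Count: 0 of 3 pathways.

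**Time-Out.** It verifies name and date of birth, but after the blood has been drawn and spun and before the marrow product exists. It does not list the product label and is not repeated at Steps 38-39. The venous and discharge SOPs state no such verification.

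**Where the exposure lies.** In the two venous pathways the drip line is attached to the patient at the draw, so the 20 ml syringe coming back from processing is the open link. In the bone marrow pathway two syringes are pooled before the bag is connected, so both syringes and the bag are open links.

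**Staff time for added checks.** Hours = participants x checks per participant x minutes per check / 60. Participants = 200 (section 12a). Minutes per check are assumed at 0.5 to 2, because the documents give none. The venous SOP has a branch for later treatment days, so one to three venous infusions per participant are taken as the range. For bone marrow, one procedure is assumed.

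- At infusion only: venous 1 to 3 checks; bone marrow 2 syringes + 1 bag = 3. Low: 200 x 1 x 0.5 / 60 = 1.7 h. High: 200 x 3 x 2 / 60 = 20 h.
- With an optional check at each draw: venous 2 to 6; bone marrow 3 + 1 = 4. Low: 200 x 2 x 0.5 / 60 = 3.3 h. High: 200 x 6 x 2 / 60 = 40 h.

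**The case against.** The sponsor could fairly say four things.

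1. **The residual risk is disclosed.** The bullet is part of a list of risks, and its preceding sentence calls administration errors a low risk. This stands. It would be wrong to report that the protocol denies the risk outright. What remains is that two adjacent sentences disagree, and the second overstates what marking does.
2. **The early part of the chain is controlled.** Staff move the blood from the draw to a cup that must be correctly labelled, which most naturally means labelled for the patient just drawn. This also stands, and it is why the gap is placed after the spin and a check at the draw is only optional. A reader might infer that the SOPs have no identity control at all; the labelling, the cup wording and the Time-Out contradict that.
3. **Other samples.** Bone marrow Step 33 asks for a processing area free of other samples. A reader might infer that the clinic foresees mix-ups or processes several patients' samples together. The step is worded as a cleanliness and contamination check, and nothing shown says that two patients' samples are handled at once. The venous and discharge SOPs also require earlier patients' materials to be cleared.
4. **The check may sit elsewhere.** Section 11e refers to further policies and procedures, policy CL-005 cites others, and the EMR step mentions checklists and flowsheets. None can be seen, so the finding is limited to the SOPs shown. The infusion steps themselves point to no such check.

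**Conclusion.** The concern holds in a limited form. Section 13 should not say that marking eliminates this risk. In the SOPs shown, no step between the spun cup and the infusion matches the product to its recipient in any of the three pathways.

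This rests on the visible text alone, and a check in an unseen form would narrow it. A reader might go further and infer that mix-ups are likely or that the trial's results are compromised. The documents support neither: they give no mix-up rate or basis for estimating one, and the FEV1 and CCQ analyses do not depend on this point. It is a participant-safety gap that can be closed cheaply.

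**What to change.** 1. In section 13, replace *eliminating* with *reducing*. Do the same in the consent if it carries the same wording.
2. Add a two-identifier check (name and date of birth) of product label against patient:
   - the labelled 20 ml syringe, immediately before injection into the bag, at venous Step 20 and discharge Step 11;
   - both syringes at bone marrow Step 38, and the labelled bag before connection at Step 39.
3. State that the 20 ml product syringe is labelled at venous Step 19 and discharge Step 10, and that the concentrate syringe and the final bag are labelled in the bone marrow SOP. Step 4 there can be read as covering them, but does not say so.
4. Record the check in the existing EMR step (venous Step 25, discharge Step 20, bone marrow Step 43).
5. Optionally, make the same check at the draw (venous Step 15 or 16, discharge Step 8, bone marrow Step 13).

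The cost is a few SOP lines and a brief check by staff already present, using identifiers the SOPs already require on the supplies: the study-wide hours worked out above. Bone marrow Step 38 does not say where pooling is done; if it is away from the patient, the syringe check means pooling at the bedside.

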## 14. ETHICAL CONSIDERATIONS

This study will be conducted in full conformance with principles of Good Clinical Practice (GCP) and within the laws and regulations of the state of Texas and the United States regarding stem cell treatment. It is the priority of the participants' interests over those of science or of society that will be safeguarded.

Informed consent for treatment is paramount. This ensures that participants can read and understand the information they need to make an informed decision about their voluntary treatment. *A copy of the informed consent is attached to this protocol.*

Patients are treated by the Lung Institute on a fee-for-service basis. This introduces an ethical consideration that the treatment is available only to those patients who can afford treatment. Therefore, results of our study and the experiences of our patients may not be generalizable to those who cannot pay for treatment. To mitigate the risk of ethical implications, patients will never be coerced into treatment, promised that they will see a definite improvement in their condition, or will be compensated for their treatment.

**PURPOSE:**

TO ENSURE THAT ALL LUNG INSTITUTE (LI) AUTOLOGOUS-ADULT STEM CELL (A-ASC) PROCEDURES ARE ADMINISTERED IN A WAY THAT IS CONSISTENT WITH QUALITY STANDARDS AND APPLICABLE REGULATORY REQUIREMENTS.

**DEFINITIONS:**

**A-ASC PROCEDURE/TREATMENT:** AN AUTOLOGOUS-ADULT STEM CELL MEDICAL PROCEDURE.

**CLINICAL STAFF:** A LICENSED PHYSICIAN OR PRACTITIONER, AND EMPLOYEE(S) WORKING BY DELEGATION THEREOF.

**EMPLOYEE (STAFF):** PERSON(S) EMPLOYED BY LUNG INSTITUTE (LI) AND/OR ITS ADMINISTRATOR AND MANAGING AFFILIATE REGENERATIVE MEDICINE SOLUTIONS (RMS). AN EMPLOYEE INCLUDES FULL-TIME, PART-TIME, TEMPORARY, VOLUNTEERS, TRAINEES, CONTRACTED/CONSULTING INDIVIDUALS, AND OTHER INDIVIDUALS WHOSE CONDUCT IS UNDER THE DIRECT CONTROL OF LI (WHETHER OR NOT THEY ARE PAID BY LI).

**EQUIPMENT:** A CLINICAL INSTRUMENT USED IN A CLINICAL SETTING.

**FACILITY:** A LUNG INSTITUTE (LI) PRACTICE LOCATION/CLINICAL SITE.

**PROVIDER/PRACTITIONER:** AN LI EMPLOYED PHYSICIAN, NURSE PRACTITIONER, OR ANY OTHER LICENSED CLINICAL STAFF MEMBER WHICH RENDERS CARE TO AN LI PATIENT; THIS INCLUDES PHYSICIAN EXTENDERS AND TEMPORARY PROVIDERS THAT HAVE BEEN APPROVED TO RENDER SERVICES AT AN LI FACILITY.

**POLICY STATEMENT:**

THE LUNG INSTITUTE (LI) WILL SET AND MAINTAIN PRACTICE STANDARDS FOR ALL A-ASC TREATMENTS ADMINISTERED TO QUALIFYING PATIENTS DIAGNOSED WITH CHRONIC OBSTRUCTIVE PULMONARY DISEASE (COPD) OR INTERSTITIAL LUNG DISEASE (ILD), OR DIAGNOSED UNDER ONE OF THE VARIOUS ILD DISORDERS/DISEASES.

A-ASC TREATMENTS:

- a. VENOUS

**PROCEDURES:**

**A. PROCEDURE INCLUSION CRITERIA**

**1. FOR ALL PROCEDURES**

- a) DIAGNOSIS OF COPD; OR
  
- b) DIAGNOSIS OF ILD AND/OR A DIAGNOSIS THAT FALLS UNDER THE VARIOUS ILD DISORDER/DISEASES; AND ILD DISORDERS/DISEASES INCLUDE, BUT ARE NOT LIMITED TO:
  - i. INTERSTITIAL PNEUMONIA
  - ii. IDIOPATHIC PULMONARY FIBROSIS AND/OR OTHER PULMONARY FIBROSIS
  - iii. SARCOIDOSIS
  - iv. NONSPECIFIC INTERSTITIAL PNEUMONITIS: INTERSTITIAL LUNG DISEASE THAT'S OFTEN PRESENT WITH AUTOIMMUNE CONDITIONS (SUCH AS RHEUMATOID ARTHRITIS OR SCLERODERMA).
  - v. HYPERSENSITIVITY PNEUMONITIS
  - vi. ASBESTOSIS
- c) MEET AGE REQUIREMENT (16 YEARS OR OLDER); AND
- d) CHEST X-RAY OR CT SCAN OF LUNGS SHOWING FIBROSIS AND/OR CHRONIC INFLAMMATION
  - i. DOCUMENTATION OF DIAGNOSIS MAY BE CAPTURED IN OTHER NOTES IF SCAN X-RAY OR SCAN IS NOT AS DESCRIPTIVE.

